#### **7.6.6. Management of Potential Hepatobiliary Toxicity**

7.6.6.1. Any subject exhibiting signs/symptoms or laboratory abnormalities suggestive of possible hepatobiliary toxicity should undergo thorough examination and clinical workup as deemed appropriate by the Investigator. Consideration should be given to appropriate imaging studies (e.g., ultrasound of the liver and biliary tree) and potential consultation with a gastroenterologist with specialty training in hepatobiliary diseases.

#### **7.7. Criteria for discontinuation of study drug**

- 7.7.1. In the event of the following, study drug will be discontinued: unacceptable toxicity, subject request for any reason, pregnancy, development of active tuberculosis, discontinue of the study at the request of the IRB
- 7.7.2. In the event of the following, study drug may be discontinued: in the event of significant new illness that compromises the ability to assess end points, lack of efficacy, subject noncompliance.
- 7.7.3. In the event that study drug is discontinued, every attempt should be made to keep the subject in the study and continue to perform the required follow ups and procedures through to the Week 16 Visit

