**6.2.4.7. Week 16 Visit**

- 6.2.4.7.1. At 16 week visit, subjects will have vitals taken, pill count will be performed; both the MAAS and HIV-SI will be completed, followed by history, symptom based physical, and laboratory exam. Pill count will be taken from bottle dispensed at baseline visit. Staff will confirm with patient that they have the commercial medication .

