**6.2.4.8. Early Discontinuation Visit**

- 6.2.4.8.1. If the subject discontinues the study drug prior to the Week 16 Visit, the subject will be asked to return to the clinic within 10 days of stopping study drug for the Early Study Drug Discontinuation Visit. Every attempt should be made to keep the subject in the study and continue to perform the required follow ups and procedures through to the Week 16 Visit. If this is not acceptable to the subject or investigator, the subject may be withdrawn from the study. In the event that the subject is not kept in the study, physical and laboratory exam, as well as the MAAS and HIV-SI should be performed unless the subject does not consent to them.

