#### 8.2.2.1. Primary Endpoint

8.2.2.1.1. Percentage of subjects reporting suboptimal adherence, analyzed by intention to treat, from baseline to 16 weeks.

8.2.2.1.1.1. *We hypothesize that a minimum of 85% of subjects taking DRV/COB/FTC/TAF will demonstrate an optimal adherence score from baseline to four-months as measured by the Midland ART Adherence Survey.* Optimal adherence is defined as a Rasch score greater than or equal to 90%. Rasch scores range from 0% (no adherence) to 100% - (perfect adherence).

8.2.2.2. Secondary Endpoints. These are descriptive endpoints so no hypotheses are tested.

8.2.2.2.1. Change at 4 months from baseline in tolerability measured by standardized patient reported outcome questionnaire

8.2.2.2.2. Percentage of subjects with greater than or equal to 90% by pill count

8.2.2.2.3. Proportion of subjects that have HIV-1 RNA  $\geq 50$  copies/mL at baseline and at month 4

8.2.2.2.4. Proportion of subjects with significant changes at 4 months from baseline in serum creatinine, AST or ALT

8.2.2.2.5. Change at 4 months from baseline in absolute and percentage CD4.

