#### 8.3.3. Intent-to-Treat:

8.3.3.1. This dataset contains derived primary and secondary endpoint variables from all subjects initially enrolled in the study. This dataset has the format of one record per subject per analysis period.

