## APPENDIX 1: Midland ART Adherence Survey (MAAS)

**Midland ART Adherence Survey**

Survey # \_\_\_\_\_

Age:  18-35  36-49  50-65  66-99      Ethnicity: \_\_\_\_\_      Gender: \_\_\_\_\_How long on ART?  <1 year       1-5 years       6-10 years       11-15 years       16 or more years

1. Do you sometimes forget to take your HIV medications?	 Yes  No	Current prescribed HIV regimen:
3. Have you ever not taken your meds because you felt worse when you took it?	 Yes  No	 Biktarvy  Genvoya  Julica  Triumeq  Isentress/Isentress HD  Stribild  Dulera  Tivicay  Syntuza  Atripla  Complera  Odefsey  Reyataz or Evotaz  Prezista or Prezcobix
4. When you travel or leave home, do you sometimes forget to bring along your medications?	 Yes  No	 Descovy  Truvada  Epzicom  Edurant  Intelence  Sustiva  Selzentry
5. Did you take your HIV medicine yesterday?	 Yes  No	
6. When you feel like your health is good, do you sometimes stop taking your medicine?	 Yes  No	
7. Do you ever miss doses of your medications because of side effects from them? If so, what side effects?	 Yes  No	

8. How often do you take your HIV medications?

- ALWAYS –never miss a dose
- ALMOST ALWAYS-miss 1-2 times a month
- USUALLY-miss 3- 5 times a month
- SOMETIMES-miss more than 5 times, but take more than 5 times a month
- RARELY-take 3- 5 times a month
- ALMOST NEVER-take 1-2 times a month
- NEVER-do not take the medication

9. How many days in the last week did you not take your HIV medication? \_\_\_\_\_

10. How many days in the last month did you not take your HIV medication? \_\_\_\_\_

11. What is your biggest issue with being able to take your medication: \_\_\_\_\_

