**6. Pregnancy**

All initial reports of pregnancy must be reported to the COMPANY by the PRINCIPAL INVESTIGATOR **within 24 hours of becoming aware of the event** using the Serious Adverse Event Form. Abnormal pregnancy outcomes (e.g. spontaneous abortion, fetal death, stillbirth, congenital anomaly, ectopic pregnancy) are considered serious adverse events and must be reported using the Serious Adverse Event Form.

Any subject who becomes pregnant during the study must be promptly withdrawn from the study and discontinue further study treatment.

Because the effect of the J&J medicinal product on sperm is unknown, pregnancies in partners of male subjects exposed to a J&J medicinal product will be reported by the PRINCIPAL INVESTIGATOR **within 24 hours of their knowledge of the event** using the Serious Adverse Event Form. Depending on local legislation this may require prior consent of the partner.

Follow-up information regarding the outcome of the pregnancy and any postnatal sequelae in the infant will be required.

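### The 85% hypothesis is about subjects taking DRV/COB/FTC/TAF, but the ITT primary would also credit good adherence to another regimen after study drug is stopped

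*Protocol*

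**What the plan says.** **Follow-up after stopping.** Protocol 7.7.3 sets the rule for subjects who come off the tablet: "every attempt should be made to keep the subject in the study and continue to perform the required follow ups and procedures". It applies up to Week 16. Section 6.2.4.8 repeats the rule and adds that, if this is not acceptable to subject or investigator, "the subject may be withdrawn from the study". The reasons for stopping in 7.7.1 and 7.7.2 include unacceptable toxicity, the subject's request, lack of efficacy and noncompliance. They also include pregnancy, active tuberculosis, an IRB request and significant new illness.

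**Measurement.** At Week 16 (6.2.4.7) "both the MAAS and HIV-SI will be completed". The MAAS (Appendix 1) asks, for example, "How often do you take your HIV medications". None of its questions is limited to study drug. The form records the currently prescribed regimen, but no scoring rule in the protocol uses that field.

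**Analysis.** The Part 2 primary (8.2.2.1 and 8.6.1) is by intention to treat. The ITT dataset (8.3.3) holds endpoint variables "from all subjects initially enrolled in the study". Optimal means a Rasch score of 90% or more, with no further condition. Drug discontinuations are counted separately, as a descriptive secondary endpoint (8.7.1.7).

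**Hypothesis.** Section 8.2.2.1 states: "We hypothesize that a minimum of 85% of subjects taking DRV/COB/FTC/TAF will demonstrate an optimal adherence score". Section 8.6.1.2 repeats it. The primary objective in 3.2.1 is broader: changes in ART adherence among subjects who switch.

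**The concern.** The Rationale (section 2) is that patients who do not tolerate integrase inhibitors may tolerate this tablet better and so adhere better. Stopping the tablet for toxicity, or being taken off it for noncompliance, is the failure the trial is meant to detect. Under the rules above, that subject can move to another regimen, take it reliably, score 90% or more at Week 16 and be counted towards a statement about subjects taking DRV/COB/FTC/TAF.

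The measure and the hypothesis therefore refer to different things. Part 2 has one arm, so no comparator offsets the difference, and with a target of 30 subjects a few cases can decide whether the observed proportion reaches 85%.

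**Working it through.** **The plan's own figure.** Section 8.8.2 gives n = ln(1 − 0.95)/ln(1 − 0.10) = 28.43, which rounds up to 29; the protocol states 30. The difference is immaterial here, and the formula contains neither a discontinuation rate nor a rule for scoring stoppers. It neither creates nor resolves the problem.

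**Inputs from the protocol.** N = 30 (6.2.2.1); target 85% (8.2.2.1); optimal = Rasch score ≥ 90%.

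**Assumptions.** The stopping rate and how stoppers score on another regimen are not given. I use stopping of 10%, 20% and 30% as a range.

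**Step 1: weight of one subject.** 1/30 = 3.3 points. Reaching 85% needs 0.85 × 30 = 25.5, so 26 optimal scores (25/30 = 83.3%; 26/30 = 86.7%).

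**Step 2: same data, two scoring rules.** Suppose d subjects stop, all d score optimal on another regimen, and the total is exactly 26/30.

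| Stoppers d | Optimal among those still on drug | MAAS as scored | Stoppers counted as not optimal |
|---|---|---|---|
| 3 | 23/27 = 85.2% | 26/30 = 86.7% | 23/30 = 76.7% |
| 6 | 20/24 = 83.3% | 26/30 = 86.7% | 20/30 = 66.7% |
| 9 | 17/21 = 81.0% | 26/30 = 86.7% | 17/30 = 56.7% |

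**Step 3: chance of observing at least 26 of 30.** Let s be the stopping rate, 0.85 the probability of an optimal score on study drug, and q that probability for stoppers. MAAS as scored gives p = 0.85(1 − s) + q·s. Counting stoppers as not optimal gives p = 0.85(1 − s). The table shows P(X ≥ 26) for X ~ Binomial(30, p).

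| s | As scored, q = 0.85 | As scored, q = 0.5 | Stoppers not optimal (same as q = 0) |
|---|---|---|---|
| 10% | p = 0.850: 0.52 | p = 0.815: 0.33 | p = 0.765: 0.134 |
| 20% | p = 0.850: 0.52 | p = 0.780: 0.18 | p = 0.680: 0.018 |
| 30% | p = 0.850: 0.52 | p = 0.745: 0.09 | p = 0.595: 0.001 |

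The gap depends on both s and q. If stoppers take no ART and score low (q near 0), the two rules agree.

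**Step 4: effect on a formal test.** Section 8.6.1.1 sets a 5% two-sided level but names no null value. If the null were 85% (an assumption), the exact binomial p-value is 0.20 for 23/30 and 1.00 for 26/30. Three such subjects would change the reported proportion but not that test. With six (20/30) the value is 0.010, so there the scoring rule would matter.

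**The case against.** The strongest reply is that nothing here is improper. Keeping subjects after they stop drug and analysing all who enrolled is ordinary intention-to-treat practice. It fits the objective in 3.2.1, which speaks of ART adherence in general. The survey must be regimen-neutral, because at baseline it measures adherence to the integrase regimen. Discontinuations, study-drug pill counts and the HIV-SI are reported separately, so a stopper would be visible. The SAP, which is not shown, may separate these subjects using the regimen field and discontinuation records.

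Most of this stands. The regimen-neutral analysis is legitimate and should be kept. It does not, however, answer the hypothesis as worded. Population, instrument, threshold and hypothesis are all fixed in the protocol itself, so the disagreement does not depend on the SAP, although the SAP could resolve it.

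A reader might infer something stronger: that the primary is biased towards success, or that stoppers as a group are counted as successes. The documents do not support that. No discontinuation rate is given. Only stoppers who do well on another regimen are affected, and those off all ART would be expected to score low. Retention is a strong aim, not a certainty. For pregnancy, Appendix 3 (section 6) says "Any subject who becomes pregnant during the study must be promptly withdrawn from the study and discontinue further study treatment", which does not agree with the retention rule in 7.7.3; the two must be reconciled.

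A reader might also conclude that every stop should count as failure. That would label subjects non-adherent when drug was stopped for pregnancy, tuberculosis or an IRB request, which says nothing about tolerance or adherence.

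**Conclusion.** The point holds as a mismatch between the stated hypothesis and the measure used to assess it. A subject who stops study drug for a reason the trial is meant to detect, and then adheres to another regimen, would count in favour of a claim about DRV/COB/FTC/TAF. Each such subject is worth 3.3 points when 30 are enrolled. The move from 76.7% to 86.7% is an illustration that assumes three stoppers, all optimal elsewhere; it is not a forecast. The actual effect is unknown and could be nil. The change is worth making because the trial is small and single-arm, and the data needed are already collected.

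**What to change.** In 8.6.1, for the 85% hypothesis:

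- Count as not optimal any subject who stopped study drug before Week 16 for toxicity or intolerance, own request, noncompliance or lack of efficacy, identified from the recorded discontinuation reason and the MAAS regimen field.
- Report beside it the regimen-neutral ITT proportion (all enrolled, MAAS as scored) as the answer to the broader ART-adherence objective in 3.2.1.
- Handle stops unrelated to tolerance or adherence, such as pregnancy, tuberculosis or an IRB request, in a sensitivity analysis that scores them both ways.

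If the sponsor prefers to keep the regimen-neutral analysis as primary, reword the hypothesis in 8.2.2.1 and 8.6.1.2 so that it speaks of ART adherence after the switch and claims nothing about adherence to DRV/COB/FTC/TAF.

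**Cost.** No new data are needed, and follow-up and the rules for stopping drug are untouched. The reported proportion may be lower. The endpoint then combines adherence with persistence on drug and overlaps the discontinuation count, so the definition of optimal in 8.2.2.1 and 8.6.1 must be amended to match. Discontinuation reasons have to be recorded well enough to classify.

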#### **7.8. Management of viral rebound**

7.8.1. At any post baseline visit either (1) an HIV-1 RNA  $\geq$  50 copies/mL for subjects who were  $<50$  at baseline or (2) an increase by 1 log for subjects who were  $\geq 50$  copies at baseline, will be repeated for confirmation within 4 weeks of the original test result. If confirmatory testing is  $\geq 200$ , HIV-1 genotype will be performed on the confirmatory sample. Subject may be withdrawn from the study at investigators discretion if resistance suggested by results. If no resistance is found, repeat viral load should be repeated again 4 weeks later.

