#### 6.2.4. Study Procedure

##### 6.2.4.1. Overview

6.2.4.1.1. Subjects who are referred for screening from Part I who meet other eligibility criteria (see table 6.2.4.2.1) will be offered enrollment in Part 2. Those who provide consent will complete HIV Symptom Index (HIV-SI), a validated Patient Reported Outcome survey to assess side effects/quality of life, undergo physical and laboratory examinations, and ART will be switched to DRV/COB/FTC/TAF (Syntuza). For subjects who were not suppressed at their last lab evaluation, an HIV genotype will be performed prior to enrollment. Subjects who do not provide consent to enroll in the study will be referred back to their provider to address issues with tolerance and adherence.

6.2.4.1.2. Subjects will be followed for 16 weeks. During that period, they will be brought back for evaluation at the 4th and 16th week. At those evaluations, they will again complete the PRO and adherence surveys to assess tolerability and adherence. At the evaluations, they will also be monitored for safety and effectiveness via physical exams and laboratory studies. See Table 6.2.4.1.2

6.2.4.1.2.1. Labs at each visit: Complete Blood Count, Complete Metabolic Panel, Urinalysis, CD4 panel, HIV1 Quantitative viral load. If subject is of childbearing potential, urine pregnancy will be performed.

6.2.4.1.2.1.1. Special situations: If HIV viral load is >200 prior to baseline and not accompanied by recent genotype, a genotype will be performed.

6.2.4.1.3. Interim analysis will be performed when all subjects have completed 1 month evaluation or when 10 subjects have completed 4 month evaluation, whichever comes first.

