**6.2.4.9. Post Study Visit**

- 6.2.4.9.1. If any significant abnormality is detected either at 4 month end of study visit or early discontinuation visit, a repeat exam and laboratories will be performed approximately 30 days following (or sooner, if PI believes to be clinically indicated) to ensure their resolution, unless at the determination of the PI they are deemed not related to the study drug.

Table 6.2.4.1.2: Overview of Study Procedures

Procedures	Screening and/or Baseline Combined Visit	Screening (if not same day as screen)	Baseline (if not same day as screen)	Week 4	Week 14 Event	Week 16	Early Discontinuation
Vitals	X	X	X	X		X	X
MAAS	X	X		X		X	X
HIV-SI	X		X	X		X	X
History and Physical	X	X					
History and Symptom based physical			X	X		X	X
Complete Blood Count	X		X	X		X	X
CD4 panel	X		X	X		X	X
Complete Metabolic Panel	X		X	X		X	X
HIV-1 Quantitative viral load	X		X	X		X	X
Urinalysis	X		X	X		X	X
Study Drug Dispensation			X	X			
Treatment Adherence and Accountability				X		X	
Commercial Script sent to Patient's Pharmacy					X		
HIV Genotype	if viral load >200 copies/mL at last check		if viral load >200 copies/mL at last check	if viral load >200 copies/mL at last check		if viral load >200 copies/mL at last check	if viral load >200 copies/mL at last check
Urine pregnancy	if indicated		if indicated	if indicated		if indicated	if indicated
Hepatitis B viral load	if indicated		if indicated	if indicated		if indicated	if indicated

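### The viral rebound rule gives no reference value for its 1-log trigger; read from baseline, it misses subjects who enter unsuppressed, suppress on study and then rebound

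*Protocol*

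**What the plan says.** Section 7.8.1 applies at any post-baseline visit and has two triggers. Trigger (1) is HIV-1 RNA of 50 copies/mL or more in a subject who was below 50 at baseline. Trigger (2) is "an increase by 1 log for subjects who were" at or above 50 at baseline. A triggering result "will be repeated for confirmation within 4 weeks of the original test result". If the confirmatory value is 200 or more, a genotype is run on that sample. "If no resistance is found, repeat viral load should be repeated again 4 weeks later".

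The schedule around this rule is short. Section 6.2.4.1.2 states: "Subjects will be followed for 16 weeks. During that period, they will be brought back for evaluation at the" fourth and sixteenth week. Under section 6.2.4.8.1, if drug is stopped early, "the subject will be asked to return to the clinic within 10 days of stopping study drug".

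Two other provisions bear on the same visits:

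- For a significant abnormality at the end-of-study or early discontinuation visit, section 6.2.4.9.1 says "a repeat exam and laboratories will be performed approximately 30 days following", but "unless at the determination of the PI they are deemed not related to the study drug".
- The genotype row of Table 6.2.4.1.2, repeated in Appendix 5, applies "if viral load >200 copies/mL at last check".

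Unsuppressed subjects can enter (section 6.2.4.1.1), and section 5.1.2 treats the drug as investigational for them.

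**The concern.** A 1-log rise has no meaning until its starting point is named. The ALT flare rule in section 7.6.5.1 does name baseline; trigger (2) names nothing. Two readers could handle the same subject differently.

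The more likely reading, from baseline, also leaves a hole. Trigger (1) is closed to anyone at or above 50 at baseline, and trigger (2) needs a full log above the entry value. A subject who enters viraemic, suppresses on the study drug and then loses suppression can stay under both. The genotype in section 7.8.1 is done on the confirmatory sample, so without a trigger that section requires neither the repeat nor the resistance test. This is the group for whom the protocol calls the drug investigational.

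**Working it through.** **Inputs from the protocol.** Triggers, 4-week repeat and genotype threshold of 200: section 7.8.1. Post-baseline viral loads at Week 4, Week 16 and early discontinuation: Table 6.2.4.1.2. Target enrolment of 30: section 6.2.2.1. The viral loads below are illustrations, not trial data.

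**1. The two readings disagree.** Take 5,000 at baseline, <50 at Week 4 and 40,000 at Week 16.

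- From baseline: log10(40,000/5,000) = 0.90, below 1, so no repeat is required.
- From the Week 4 value: log10(40,000/50) = 2.90, a lower bound because Week 4 is below 50, so a repeat is required.

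**2. Range outside the trigger on the baseline reading.** Trigger (2) fires at 10 × baseline (B). A rebound from 50 up to just under that value is not covered; the width is log10(10B/50).

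| Baseline B | Not covered | Width (log10) |
|---|---|---|
| 50 | 50 to <500 | 1.0 |
| 200 | 50 to <2,000 | 1.6 |
| 5,000 | 50 to <50,000 | 3.0 |
| 20,000 | 50 to <200,000 | 3.6 |

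**3. Unevenness at the cut-point.** Take two subjects, both <50 at Week 4. One goes from 49 at baseline to 50 at Week 16: log10(50/49) = 0.009, and a repeat is required under trigger (1). The other goes from 50 at baseline to 499 at Week 16: log10(499/50) = 0.999, and no repeat is required under trigger (2).

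**4. When it can occur.** Suppression followed by rebound needs two on-study values, and Week 4 is the first. Apart from unscheduled tests, the case can therefore appear only at Week 16 or at an early discontinuation visit.

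**5. How many subjects.** The protocol gives no rates. Assumed: 10% to 50% of 30 enter at 50 or more (3 to 15); 30% to 60% of these are <50 at Week 4; 10% to 20% of those rebound to below 10 × baseline.

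- Low: 3 × 0.30 × 0.10 = 0.09.
- Middle: 9 × 0.45 × 0.15 = 0.61. The chance of no such subject is (1 − 0.45 × 0.15)^9 = (1 − 0.0675)^9 = 0.53.
- High: 15 × 0.60 × 0.20 = 1.8, which multiplies three maxima.

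These are subjects outside the section 7.8.1 trigger, not subjects without a retest. If a further 10% to 50% (assumed) are waived or judged not significant under section 6.2.4.9.1, the number with no repeat is 0.09 × 0.10 = 0.009 to 1.8 × 0.50 = 0.9.

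**The case against.** The strongest reply is that harm needs several readings to go the wrong way at once. Under a heading about rebound, a rise from the on-study low is also a fair reading; from a low of 49 or 20 it fires at 490 or 200, and both the 40,000 and the 499 examples would trigger. If the genotype row counts the viral load drawn at that same visit, any value above 200 goes straight to genotyping. A jump from <50 to 40,000 would hardly be judged insignificant under section 6.2.4.9.1. Appendix 3 section 5 makes lack of effect a reportable special situation, and section 7.7.2 allows discontinuation for lack of efficacy. Viraemia at an early discontinuation visit may simply reflect being off drug. Finally, a two-group rule always jumps at its boundary, and a wider tolerance for subjects viraemic at entry can be defended.

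Much of this stands as a limit on size. The gap is narrow, an obvious rebound is unlikely to go unnoticed, and the counts rest on assumptions. It does not remove the defect. None of these provisions requires a confirmatory viral load: the 30-day repeat leaves significance undefined, does not name viral load and can be waived as unrelated to drug, which is an available ground if the rebound is put down to missed doses. The genotype row is not clearly met when the last check was a suppressed Week 4 value. Even the on-study-low reading leaves a subject with 49 at Week 4 uncovered from 50 up to 490, where a subject below 50 at baseline would be repeated at 50.

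**Conclusion.** The point holds as a minor safety clarification. Trigger (2) lacks a reference value, and on its natural reading it does not require confirmation of lost suppression in subjects who entered at 50 or more and rebound to below 10 times baseline. What remains uncovered is a rebound at Week 16 or early discontinuation that the PI waives as unrelated or does not judge significant. On the assumed rates that is about 0.01 to 0.9 subjects out of 30; the existence of the gap follows from the text, but its frequency does not. No endpoint changes: section 4.2.2.2 uses the Week 16 value whether or not it is repeated. Sample size and analysis are untouched.

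**What to change.** Amend trigger (2) of section 7.8.1 to read: *HIV-1 RNA ≥50 copies/mL after any on-study value <50, or an increase of ≥1 log10 from the lowest value at or after baseline, for subjects ≥50 copies/mL at baseline.*

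Naming baseline alone would settle the ambiguity but keep the gap; the first limb closes it. No existing trigger is lost, because the lowest value at or after baseline cannot exceed baseline. Section 7.8.1 already applies at any post-baseline visit, so a cross-reference in section 6.2.4.9 is optional. The genotype threshold of 200, the genotype row and the endpoints can stay.

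**Cost.** One line of amendment. Each added case needs one repeat within 4 weeks (16 + 4 = about Week 20 for a Week 16 rebound, close to the existing 30-day repeat). If that is 200 or more, it also needs a genotype and, where no resistance is found, a second draw at about Week 24 (20 + 4). At the upper assumption this is 1.8 × 2 = 3.6 draws and 1.8 genotypes. Some repeats will be for transient low values, as trigger (1) already accepts. The second limb also brings in partial responders, who are not in this count: 20,000, then 300, then 5,000 is log10(5,000/300) = 1.22 above the lowest value. If the sponsor does not want them included, that limb can be measured from baseline instead, and the first limb still closes the gap described here.
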